## 8.6 Electrocardiogram

ECG measurements including PR, QRS, QT and RR are taken from three consecutive complexes (representing three consecutive heart beats). The mean value of the available ECG measurements will be calculated and used in the summary table. For the calculation of QT correction by heart rate, QTc is considered as missing only if all three consecutive beats are unreadable. For each ECG, QT and RR intervals from three consecutive complexes (representing three consecutive heart beats) will be measured manually. The QT correction is performed on beat-to-beat basis. The mean of ratios (beat-to-beat) is calculated by  $(QTc1 + QTc2 + QTc3)/3$  using each QT-RR pair: (QT1, RR1), (QT2, RR2) and (QT3, RR3). The corrected QT intervals for QTcB, QTcF, and QTcN are defined as follows:

- QTcB is the length of the QT interval corrected for heart rate by Bazett's formula:  $QTcB = QT / (RR)^{1/2}$ ,
- QTcF is the length of the QT interval corrected for heart rate by Fredericia's formula:  $QTcF = QT / (RR)^{1/3}$ ,
- QTcN is the length of the QT interval corrected for heart rate by the FDA Neuropharm Division formula:  $QTcN = QT / (RR)^{0.37}$ .

Potentially clinically relevant ECG abnormalities will be listed by subject. The criteria for potentially clinically relevant ECG abnormalities are provided in [Appendix 3](#). Incidences of abnormal ECGs of potential clinical relevance, based on the observations during scheduled and unscheduled post-baseline visits will be tabulated by treatment formulation and disease type. Descriptive statistics of change from baseline in ECG intervals of PR, QRS, RR, QT and QTc, will be presented by trial visit, treatment formulation and disease type. In addition, incidences of categorical change in ECG - QTc will be provided for the following categories: change from baseline  $>30$  millisecond (MS) to  $<60$  MS, change from baseline  $\geq 60$  MS, new onset  $>450$  MS, new onset  $>480$  MS and new onset  $>500$  MS.

Protocol 031-201-00181

If ECG assessments are repeated for the same trial visit, the last repeated values will be used for generation of mean change from baseline. This is accomplished by sorting patient data by visit date and visit time (if applicable) within the same trial visit.

## 8.7 Suicidality

Suicidality data collected from the C-SSRS assessments will be summarized by treatment formulation and disease type in incidence of suicidality; suicidal behavior only, emergence of suicidal behavior; suicidal ideation only, emergence of suicidal ideation, emergence of serious suicidal ideation, and worsening of suicidal ideation at trial visits and last visit in addition to overall during the treatment phase.

Suicidality is defined as reporting any suicidal ideation or behavior. Suicidal behavior only is defined as reporting any type of suicidal behaviors (actual attempt, interrupted attempt, aborted attempt and preparatory acts or behavior) throughout assessment period. Emergence of suicidal behavior is defined as having no suicidal behavior at baseline and reporting any type of behavior at post-baseline. Suicidal ideation only is defined as reporting any type of suicidal ideation. Emergence of suicidal ideation is defined as having no suicidal ideation at baseline and reporting any type of ideation during treatment. Emergence of serious suicidal ideation is defined as having no suicidal ideation at baseline and reporting serious suicidal ideation with score of 4 or 5 on suicidal ideation severity rating during the treatment. In assessment of suicidal ideation and level of severity, each person is given a score of 0 (no ideation present) to 5 (active ideation with plan and intent). Worsening of suicidal ideation is defined as having greater severity of ideation for the most severe suicidal ideation at post baseline than at baseline. Numbers of patients reporting suicidal behavior are also reported by type of suicidal behavior.

Descriptive statistics of the incidence of suicidality and incidence of suicidality by type (suicidal behavior and suicidal ideation), as well as the mean changes of Suicidal Ideation Intensity (SSI) total scores for most severe ideation from baseline will be reported by trial visit, treatment formulation and disease type. The suicidal ideation intensity total score is the sum of suicidal ideation severity rating scores for frequency, duration, controllability, deterrents and reasons for ideation. For each item, each subject gets intensity score from 0 (none) to 5 (worst). Therefore, SSI total score is a range from 0 to 25. If the subject did not endorse any suicidal ideation, a score of 0 is given for the intensity scale.

There are 9 categories for Columbia Classification Algorithm of Suicide Assessment (C-CASA) method, which are coded as below,

1. completed suicide;

Protocol 031-201-00181

2. suicide attempt;
3. preparatory actions toward imminent suicidal behavior;
4. suicidal ideation;
5. self-injurious behavior, intent unknown;
6. not enough information: death;
7. non-suicidal self-injurious behavior;
8. other (Accident; Psychiatric, Medical);
9. not enough information: non-death.

Data collected from C-SSRS will be mapped into C-CASA category as specified in [Table 8.7-1](#). Incidence of potential suicidality events using C-CASA category will be provided for safety sample.

C-SSRS	C-CASA Category
Completed Suicide	1. Completed Suicide
Actual Attempt	2. Suicide Attempt
-Interrupted Attempt -Aborted Attempt -Preparatory Acts or Behavior	3. Preparatory Actions Toward Imminent Suicidal Behavior
1. Wish to Die 2. Non-Specific Active Suicidal Thoughts 3. Active Suicidal Ideation with Any Methods (Not Plan) without Intent to Act 4. Active Suicidal Ideation with Some intent To Act, without Specific Plan 5. Active Suicidal Ideation with specific Plan and Intent	4. Suicidal Ideation
Non-suicidal Self-injurious Behavior	7. Non-suicidal Self-injurious Behavior

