Note: Activities designated with superscript b are those performed in subjects randomized to aripiprazole 2M LAI 960 mg; activities designated with superscript i are those performed in subjects randomized to aripiprazole IM depot 400 mg. Activities without subscripts are performed in all subjects.

aSubjects can be admitted to the clinic on Day -1, but tests and assessments are to be done on Day 1.

bSubjects who receive aripiprazole 2M LAI 960 mg.

cIf tolerability to aripiprazole must be established, there will be a 3-day assessment of oral aripiprazole tolerability during the screening period. At the discretion of the investigator, subjects **may** be housed in the unit for the assessment. Subjects having tolerability assessed as outpatients **must** be contacted by the site each day during the assessment period.

dSubjects may be housed in the clinical unit for up to 21 days following administration of the first dose of IMP, but **only** at the discretion of the investigator. Subjects who are outpatients during the 7- to 14-day oral overlap period **must** be contacted by the site every day during this period.

eFemale subjects of childbearing potential only. If the urine pregnancy test is positive, the result should be confirmed with a serum pregnancy test which may be performed by a local laboratory.

fPerimenopausal and postmenopausal female subjects only.

gVital signs will include systolic and diastolic blood pressure, heart rate, and body temperature. Vital signs will be obtained prior to PK blood draws and ECGs at the nominal time points, where applicable. At each time point, blood pressure (systolic and diastolic) and heart rate will be taken after subjects have been in the supine position for at least 5 minutes and again after subjects have been standing for 2 minutes, but not more than 3 minutes. Body temperature will be taken with the subject in the supine position (ie, only once).

hThe Baseline/Screening version of the C-SSRS will be administered at the screening visit and the Since Last Visit version of the C-SSRS will be administered at all other time points.

iSubjects who receive aripiprazole IM depot 400 mg.

jAll efficacy assessments will be performed prior to PK blood draws and dosing, where applicable.

Protocol 031-201-00181

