**Table 3.7.3-2 Sparse Sampling Schedule Trial Days and Activities**

| Days 36, 43, and 50 ± 2 days (outpatient, subjects receiving aripiprazole 2M LAI 960 mg)   |  |
|---|--|
| 
 
• Document birth control methods.
 
• Record concomitant medications and review for prohibited or restricted medications.
 
• Record adjustment of current oral antipsychotic, mood stabilizer, or antidepressant therapy.
 
• Assess and record AEs.
 
• Take vital signs (systolic and diastolic blood pressure, heart rate, and body temperature).
 
• Administer the Since Last Visit version of the C-SSRS.
 
• Draw a PK blood sample between 8 AM and 2 PM.
 
  |  |
| Day 57 ± 2 days (outpatient, all subjects)   |  |
| 
Predose:
 
 
• Document birth control methods.
 
• Record concomitant medications and review for prohibited or restricted medications.
 
• Record adjustment of current oral antipsychotic, mood stabilizer, or antidepressant therapy.
 
• Assess and record AEs.
 
• Perform a urine pregnancy test (FOCBP only).
 
• Measure weight.
 
• Take vital signs (systolic and diastolic blood pressure, heart rate, and body temperature).
 
• Administer a 12-lead safety ECG in triplicate (5 minutes apart).
 
• Administer the Since Last Visit version of the C-SSRS.
 
• Assess EPS (SAS, AIMS, and BARS).
 
• Administer the PANSS (schizophrenia subjects only).
 
• Administer CGI-S scale, CGI-I scale, and SWN-S (all subjects).
 
• Administer the MADRS, YMRS, and CGI-BP (bipolar subjects only).
 
• Draw a PK blood sample (within 2 hours prior to dosing).
 
• Assessment and confirmation by the investigator that the injection site is appropriate 30 minutes prior to IMP injection.
 
• Have subjects complete a VAS of the level of perceived pain at the injection site completed approximately 30 minutes prior to IMP injection.
 
• Administer IMP.
 
 |  |
| 
Postdose:
 
 
• Have subjects complete a VAS of the level of perceived pain at the injection site approximately 1 hour (± 15 minutes) postdose.
 
• Assessment of the injection site by the investigator completed approximately 1 hour (± 15 minutes) postdose.
 
  |  |

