**Days 176, 183, and 190  $\pm$  2 days (outpatient, subjects receiving aripiprazole 2M LAI 960 mg)**

- Document birth control methods.
- Record concomitant medications and review for prohibited or restricted medications.
- Record adjustment of current oral antipsychotic, mood stabilizer, or antidepressant therapy.
- Assess and record AEs.
- Take vital signs (systolic and diastolic blood pressure, heart rate, and body temperature).
- Administer the Since Last Visit version of the C-SSRS.

Protocol 031-201-00181

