**Table 3.7.3-3 Robust Sampling Schedule Trial Days and Activities**

- Administer the Since Last Visit version of the C-SSRS to subjects randomized to aripiprazole IM Depot 400 mg only on Day 218.
- Administer the Since Last Visit version of the C-SSRS to subjects randomized to aripiprazole 2M LAI 960 mg on each outpatient Days 204, 211, and 218.
- Draw a PK blood sample between 8 AM and 2 PM.
- Discharge subjects randomized to aripiprazole IM Depot 400 mg from the clinical unit after completing all activities (Day 218).

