### **3.7.6.5      *Columbia-Suicide Severity Rating Scale***

Suicidality will be monitored during the trial using the C-SSRS. The Baseline/Screening version and the Since Last Visit version of the C-SSRS will be completed by trained trial site staff at the time points presented in the schedule of assessments ([Table 3.7-1](#) for sparse sampling and [Table 3.7-2](#) for robust sampling). This scale consists of a baseline evaluation that assesses the lifetime experience of the subject with suicide events and suicidal ideation and a postbaseline evaluation that focuses on suicidality since the last assessment.

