## 5.2 Trial Week Windows

The actual assessment date is mapped into the trial week. The definition of trial weeks for primary PK variables are described in [Table 5.2-1](#) and the definitions of trial weeks for efficacy scales and safety scales such as Extrapyramidal Symptoms (EPS) rating scales are included in [Table 5.2-2](#) and [Table 5.2-3](#). Trial days are derived from the formula: Trial Day = Date of assessment - Date of 1st IMP injection + 1. Based on the number of trial days, subjects are mapped to the corresponding trial week. For safety and efficacy variables, only the last observation within the same mapped trial week is used for imputing data on the following trial weeks in the derived last observation carried forward (LOCF) dataset. In addition, only last observations within the same mapped weeks are reported in the summary tables by trial week.

Table 5.2-1 Time Window for Trial Weeks for Primary PK Variables C28 and C56		
Scheduled Visit (Day)	Mapped Week (Trial Week)	Week Window (Trial Day Range ± 2 days)
197	28 (28 days after the 7th injection of 400 mg Abilify Maintena)	195-199
225	32 (28 days after the 8th injection of 400 mg Abilify Maintena or 56 days after the 4 th injection of 960 mg aripiprazole 2M LAI)	223-227

Table 5.2-2 Time Window for Mapping Trial Week for Efficacy Variables		
Scheduled Visit (Day)	Mapped Week (Trial Week)	Week Window (Trial Day Range)
1	Baseline	≤1 (before first IMP)
29	4	2-43
57	8	44-85
113	16	86-141
169	24	142-183
197	28	184-211
225	32	212-239

Protocol 031-201-00181

Table 5.2-3 Time Window for Mapping Trial Week for Safety Variables		
Scheduled Visit (Day)	Mapped Week (Trial Week)	Week Window (Trial Day Range)
1	Baseline	≤1 (before first IMP)
8	1	2-11
15	2	12-18
22	3	19-25
29	4	26-43
57	8	44-71
85	12	72-99
113	16	100-127
141	20	128-155
169	24	156-183
197	28	184-211
225	32	212-239

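### At Days 57 and 197 (and Day 218 in the robust schedule) the C-SSRS looks back over a shorter period in the 960 mg arm than in the 400 mg arm, so SAP 8.7's by-visit suicidality rates are not comparable between arms at those visits

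*SAP*

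**What the plan says.** Suicidality measured by the C-SSRS is one of the primary safety variables (Protocol 3.5.1.1; SAP 6.1). The schedule footnotes say that "the Since Last Visit version of the C-SSRS will be administered at all other time points", that is, at every visit after screening. Protocol 3.7.6.5 describes "a postbaseline evaluation that focuses on suicidality since the last assessment".

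The assessment days differ by arm. In the sparse schedule (Protocol Table 3.7.3-2) one set of visits is headed "Days 36, 43, and 50 ± 2 days (outpatient, subjects receiving aripiprazole 2M LAI 960 mg", and "Days 176, 183, and 190" are likewise for that arm only. In the robust schedule (Table 3.7.3-3), Days 36, 43 and 50 are again for the 960 mg arm only, as is the Day 190 form. On Days 204, 211 and 218 the 960 mg arm is assessed each time and the 400 mg arm only on Day 218.

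SAP 8.7 tabulates incidence, emergence and worsening by treatment and disease type, including "worsening of suicidal ideation at trial visits and last visit in addition to overall during the treatment phase". Protocol 7.6.5.1 asks for the same at each visit, at last visit and overall. Neither document mentions the length of the look-back period. For safety variables in general, SAP 5.2 says that "only last observations within the same mapped weeks are reported in the summary tables by trial week".

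**The concern.** A form that records events since the previous form yields a count over an interval, not a state on a day. If that interval is four times longer in one arm, the percentage positive at that visit is not the same quantity in the two arms. The by-visit table would set the two percentages side by side with nothing to show this.

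The direction matters: at the affected visits the shorter window belongs to the test product, so a lower rate on 960 mg could come from the visit schedule alone. The same problem affects reading down a column, because the window length changes during follow-up within each arm.

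**Working it through.** **Inputs.** Scheduled post-baseline C-SSRS days, from Protocol Tables 3.7-1, 3.7-2, 3.7.3-2 and 3.7.3-3:

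- Sparse 960 mg (20 forms): 8, 15, 22, 29, 36, 43, 50, 57, 85, 113, 141, 169, 176, 183, 190, 197, 204, 211, 218, 225
- Sparse 400 mg (14): 8, 15, 22, 29, 57, 85, 113, 141, 169, 197, 204, 211, 218, 225
- Robust 960 mg (16): 22, 29, 36, 43, 50, 57, 85, 113, 141, 169, 190, 197, 204, 211, 218, 225
- Robust 400 mg (10): 22, 29, 57, 85, 113, 141, 169, 197, 218, 225

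**Step 1: look-back window = day of form minus day of previous form** (Day 1 precedes the first).

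| Visit | Sparse 960 v 400 mg | Robust 960 v 400 mg |
|---|---|---|
| 8, 15 | 7 v 7 | no form |
| 22 | 7 v 7 | 21 v 21 |
| 29 | 7 v 7 | 7 v 7 |
| **57** | **7 v 28** | **7 v 28** |
| 85, 113, 141, 169 | 28 v 28 | 28 v 28 |
| **197** | **7 v 28** | **7 v 28** |
| 204, 211 | 7 v 7 | 7 v no form |
| **218** | 7 v 7 | **7 v 21** |
| 225 | 7 v 7 | 7 v 7 |

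The windows sum to 225 − 1 = 224 days in all four groups.

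**Step 2: size at equal true risk.** The documents give no C-SSRS event rate, so a range is assumed: probability p28 of a positive form over 28 days, the same in both arms, with a constant rate and no persistence. Then p7 = 1 − (1 − p28)^(1/4) and p21 = 1 − (1 − p28)^(3/4).

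| p28 | p7 | p28/p7 (Days 57, 197) | p21/p7 (robust Day 218) |
|---|---|---|---|
| 1% | 0.25% | 3.98 | 2.99 |
| 2% | 0.50% | 3.97 | 2.98 |
| 5% | 1.27% | 3.92 | 2.96 |
| 10% | 2.60% | 3.85 | 2.92 |

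At 2% and 129 per arm, expected positives at Day 57 are 129 × 0.02 = 2.6 (400 mg) against 129 × 0.00504 = 0.65 (960 mg).

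**Step 3: persistence.** Let a share f of the 7-day positives be subjects who are positive in every window. Then p28 = 1 − (1 − f·p7)(1 − (1 − f)·p7)^4. With p7 = 1.27%, the ratio is 3.9 at f = 0, 3.2 at 0.25, 2.5 at 0.5, 1.7 at 0.75 and 1.0 at f = 1.

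**Step 4: the mapped-week rule, if it were applied to the C-SSRS.** Keep the last form in each Table 5.2-3 window and add up the windows of the retained forms:

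- Sparse 960 mg: eight 7-day forms and three 28-day forms = 56 + 84 = 140 of 224 days (62.5%)
- Sparse 400 mg: six 7-day and five 28-day = 42 + 140 = 182 (81.3%)
- Robust 960 mg: 21 + four 7-day + four 28-day = 21 + 28 + 112 = 161 (71.9%)
- Robust 400 mg: 21 + two 7-day + six 28-day = 21 + 14 + 168 = 203 (90.6%)

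**The case against.** Four points on the other side have force.

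- **Scope.** A reader might infer that by-visit rates differ between arms throughout and drift over time. They do not. At common nominal visits the arms differ only at Days 57 and 197 and at robust Day 218, and the change over time is a step. Nor is the overall row the only sound output. The completers' last visit is Day 225, with 7 days in both arms, and the C-CASA incidence in SAP 8.7 has no stated by-visit split.
- **Size.** It is tempting to say that the tables would show the 400 mg arm as worse by a factor of 4. That needs a rate that the documents do not give, and events that do not persist. Counts would also be small. With binomial counts at p28 = 2%, the 400 mg arm shows strictly more positives at Day 57 in about 79% of trials with 129 per arm, and about 69% with 85. At 1% these fall to 62% and 50%.
- **Lost events.** A reader might infer from SAP 5.2 that positive forms vanish from the tables. The documents do not settle this. That rule governs tables by trial week, and SAP 8.7 speaks of trial visits, whereas SAP 8.8 on EPS says trial week. On the other hand, Table 5.2-3 is titled for safety variables, and SAP 8.5 refers to a mapped trial visit. With nominal visits nothing is lost: the extra forms sit in columns that have no 400 mg comparator.
- **Weight.** The tables are descriptive. No test, error rate or PK conclusion depends on them.

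These points narrow the concern but leave the mismatch at the named visits, which neither document acknowledges.

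**Conclusion.** The concern holds in this limited form. At Days 57 and 197 in both schedules, and at Day 218 in the robust schedule, by-visit incidence, emergence and worsening are not comparable between arms, and at equal true risk the artefact favours the test product. The window lengths follow directly from the schedule. The ratio of up to about 4 (about 3 at robust Day 218) rests on an assumed low, constant and equal rate; it is about 2.5 if half of the 7-day positives persist, and 1 if all do. Visits within ±2 days and unscheduled forms change individual gaps but not the pattern.

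Within each arm, the change from short windows (7 days in sparse, 21 then 7 in robust) to 28 days and back means that a rise mid-trial and a fall at the end could appear without any change in risk.

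The overall treatment-phase incidence, the completers' last visit and the C-CASA table are not distorted between arms by window length. The coverage of 140 v 182 days (sparse) and 161 v 203 (robust), 960 mg v 400 mg, applies only if the mapped-week rule is used for the C-SSRS. This is worth correcting because suicidality is a primary safety variable.

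**What to change.** In SAP 8.7:

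1. Base the between-arm comparison on eight common 28-day intervals ending at the nominal Day 29, 57, 85, 113, 141, 169, 197 and 225 visits. All four groups have a form on each of these days, so the windows in every interval sum to 28 days (for example 21 + 7 to Day 197 in robust 960 mg, and one 28-day form in robust 400 mg). Count a subject as positive if any form in the interval is positive, and use the worst severity and intensity.
2. Assign forms by nominal visit, not by actual trial day. Otherwise a Day 57 form completed on Day 58 or 59 would move into the next interval. The 400 mg subject would then have no form in the earlier interval, while a 960 mg subject would still have Days 36, 43 and 50.
3. Keep the by-visit tables, which Protocol 7.6.5.1 requires, and add a footnote giving the look-back window by arm and schedule at Days 57 and 197 and robust Day 218.
4. State that the last-observation rule of SAP 5.2 does not apply to the C-SSRS, and keep the overall row.

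The cost is SAP wording and some extra tables; no new data are needed. One limit remains and should be noted: the 960 mg arm is questioned more often (20 v 14 forms in sparse, 16 v 10 in robust; four forms against one in the interval ending at Day 57), which could affect ascertainment.

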### **8.8 Extrapyramidal Symptoms Scales**

Extrapyramidal Symptoms (EPS) rating scales include the Simpson-Angus Scale (SAS), Barnes Akathisia Rating Scale (BARS) and Abnormal Involuntary Movement Scale (AIMS). The variables to be analyzed are,

- Change from Baseline in SAS Total Score,
- Change from Baseline in BARS Global Score,
- Change from Baseline in AIMS Movement Rating Score.

The SAS total score (range 10 - 50) is the sum of the rating scores for 10 items from the SAS panel in the Case Report Form (CRF). The BARS global score (range 0 - 5) is derived from the global clinical assessment of akathisia from the BARS panel in the CRF. The AIMS movement rating score (range 0 - 28) is the sum of the rating scores for facial and oral moments (i.e., item 1 - 4), extremity movements (i.e. item 5 - 6), and trunk movements (i.e. item 7). A missing value of any item for the SAS or the AIMS movements scale could result in a missing SAS total score or AIMS movement rating

Protocol 031-201-00181

score. LOCF missing data imputation will be performed those scores. Descriptive statistics of the EPS rating scales for both LOCF and OC data and the mean changes of the scales from baseline will be reported by trial week, treatment formulation and disease type.

